Study Drug	Nitrous oxide (laughing gas). This is an FDA-approved general anesthetic and sedative agent used in hospitals and dentist offices. The use of nitrous oxide to treat bipolar depression is off-label and outside of the approved indication. Nitrous oxide will be administered under supervision of an attending-level anesthesiologist and according to standards set by the American Society of Anesthesiologists.
Intervention	Patients will receive a titrated mix of either 50% nitrous oxide/50% oxygen or "placebo" (50% nitrogen [inert]/50% oxygen) for 1 hour.
Study Design	Prospective, randomized, placebo-controlled trial using the Sequential Parallel Comparison Design. In the first stage , patients will receive 3 randomized 1-hour treatments of either nitrous oxide (25% patients) or placebo (nitrogen in air; 75% patients) every other day (e.g., M,W,F). In the second stage , participants assigned to placebo in Stage 1 will be randomized to three 1-hour treatments every other day (e.g., M,W,F) for one week, to either nitrous oxide (50% patients) or placebo (50% patients). Participants assigned to nitrous oxide in Stage 1 will remain on nitrous oxide in Stage 2. Assessments will be performed prior to each treatment series (baseline) and approximately 24 hours after inhalation sessions #1 and #2, and approximately 72 hours after inhalation session #3. One and two week assessments of continued efficacy will be made for exploratory evaluation, but not included in the primary efficacy analysis.

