Inclusion and Exclusion Criteria	Inclusion Criteria Adults 18-75 years of age Treatment-resistant bipolar depressive disorder without psychosis and a MADRS baseline score of >20. All patients must have history of being on a serum-verified (at time of entry into study) mood stabilizer [lithium at 0.5-1.2mEq/L; or valproic acid, 50-125mcg/ml] or another mood stabilizer verified through medical records for 4 weeks prior to entry into the study and remain on this mood stabilizer during the course of the trial. Further, subjects will have failed two adequate dose/duration antidepressant courses in their lifetime, including one in the current depressive episode (verified by Antidepressant Treatment History Form). Good command of the English language Exclusion Criteria Schizophrenia Schizoaffective disorder Obsessive-compulsive disorder or panic disorder Active or recent substance abuse or dependence (in remission at least 1 year prior to the study; exception = nicotine use disorders) A diagnosis of personality disorder that may interfere with the patient's ability to improve on nitrous oxide as determined by study investigator Acute medical illness that may pose subject at risk during nitrous oxide administration (neurological disorders or medical disorders including dementia, stroke, encephalopathy, Parkinson's Disease, brain tumors, multiple sclerosis, seizure disorder, severe cardiac disease, any disease known to affect drug metabolism and excretion, i.e. renal or liver disease) per P.I. discretion Active suicidal intention (inability to contract for safety) Patients with significant pulmonary disease and/or requiring supplemental oxygen

	j) Contraindication against the use of nitrous oxide: pneumothorax; bowel obstruction; middle ear occlusion; elevated intracranial pressure; chronic cobalamin and/or folate deficiency treated with folic acid or vitamin B ₁₂ ; pregnant patients; breastfeeding women; previous administration of NMDA-receptor antagonists (e.g., ketamine); current electro-convulsive therapy treatment
Primary Outcome	Change in depressive symptoms on MADRS scale between baseline and day 7 follow-up
Measurements	a) MADRS; b) Ham-D17; c) Young Mania Rating Scale (YMRS); d) Profile of Mood States Brief, 2 nd edition (POMS 2); e) Quick Inventory of Depressive Symptoms-Self Report (QIDS –SR); f) Brief Psychiatric Rating Scale (BPRS); g) Scale for Suicidal Ideation (SSI); h) Clinician Administered Dissociative States Scale (CADSS)

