7.1. Follow-Up

Assessments will be performed before and after (approximately 1 and 24 hours) each treatment, with the exception of the 3rd inhalation treatments in each Stage which will be monitored at approximately 72 hours from last inhalation session. Additional follow-up visits will be scheduled approximately one and two weeks following completion of the final gas inhalation session in any study stage (to assess for lasting efficacy of nitrous effects). However, only the two 24 hour and one 72 hour measures will be used in the statistical analysis of efficacy. The one and two week assessments will be performed to obtain preliminary information regarding lasting efficacy.

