The primary outcome variable is the change from baseline in MADRS scores during the first study week in each Stage of the SPCD study. Stage-wise test statistics representing the active vs. placebo response will be combined with equal weights for each Stage. The full analysis set is defined as all patients who were randomized and had at least one treatment dose as well as one post-baseline efficacy assessment in Stage 1. In Stage 2, the placebo non-responders who were re-randomized and had at least one treatment dose as well as one post-baseline efficacy assessment contribute to the full analysis set. A mixed model for repeated measurements (MMRM) with an unstructured variance-covariance matrix will be used for the primary efficacy analysis. This direct likelihood model is the missing data handling method recommended by the National Research Council of the National Academies of Science report on prevention and handling of missing data.

Secondary outcomes, expressed as change from baseline at 72 hours after the 3rd and final inhalation treatment will also be evaluated using the data from the full analysis set, consisting of all-comer participants from **Stage 1** and placebo non-responders in **Stage 2**. The secondary efficacy endpoints include changes in Ham-D17, Young Mania Rating Scale (YMRS), POMS, 2nd edition, and QIDS – SR. Intra- and inter-individual comparison of scores on depression scales will be done using a repeated-measures mixed effects model.

Based on our pilot study where we saw a significant reduction in depression scores among 20 unipolar depressed patients, we decided to enroll 64 patients in this trial which is similar (or larger) than previous studies of rapid antidepressants in this patient population.

10. Risk Assessment

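### Do the Synopsis (day 7) and Section 9 (first study week) leave the primary MADRS comparison open?

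*Combined protocol and SAP*

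**What the plan says.** - **Synopsis, Primary Outcome:** "Change in depressive symptoms on MADRS scale between baseline and day 7 follow-up".
- **Section 9:** the primary variable "is the change from baseline in MADRS scores during the first study week in each Stage of the SPCD study". On the model: "A mixed model for repeated measurements (MMRM) with an unstructured variance-covariance matrix will be used for the primary efficacy analysis". Stage-wise statistics are then combined with equal weights. No visit term or tested contrast is given.
- **Section 9, secondary outcomes:** these are "expressed as change from baseline at 72 hours after the 3rd and final inhalation treatment".
- **Section 7.1:** "only the two 24 hour and one 72 hour measures will be used in the statistical analysis of efficacy", so three post-baseline measures per Stage enter the model.
- **Synopsis, Study Design:** the Stage 2 course is "three 1-hour treatments every other day (e.g., M,W,F) for one week", and Stage 1 has the same spacing. On the later visits: "One and two week assessments of continued efficacy will be made for exploratory evaluation, but not included in the primary efficacy analysis".

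**The concern.** An MMRM on three visits can report the treatment difference at the last visit or the difference averaged over visits. Section 9 describes the primary variable by a period and chooses neither. It does attach a visit to the secondary outcomes, which could suggest that the primary was meant to be something else.

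The two contrasts answer different questions. One is the effect still present 72 hours after the course. The other is the mean effect over the week, including 24 hours after only one or two sessions. A rapid effect that fades favours the average, and one that builds over sessions favours the last visit. If the choice were really open, it could be made after the data were seen, in a trial of 64 patients with one primary test.

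**Working it through.** **1. Calendar.** Count the first session as day 0, with sessions on days 0, 2 and 4.

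| Assessment | Day | In the efficacy analysis? |
|---|---|---|
| 24 h after session 1 | 0 + 1 = 1 | yes |
| 24 h after session 2 | 2 + 1 = 3 | yes |
| 72 h after session 3 | 4 + 3 = 7 | yes |
| one week after session 3 | 4 + 7 = 11 | no |
| two weeks after session 3 | 4 + 14 = 18 | no |

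The day 7 visit of the Synopsis is therefore the 72-hour visit. If the first session is called day 1, these become days 2, 4, 8, 12 and 19. The 72-hour visit is still the nearest to day 7, and the two later visits are excluded by the Synopsis and Section 7.1.

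**2. One reading that fits every passage.** Three visits enter the MMRM (Section 7.1), the model is as in Section 9, and the test is at day 7 (Synopsis). Day 7 closes the first study week, so the Section 9 wording is met too. A last-visit test still uses all three visits, because the earlier ones inform the estimate when data are missing. A visit average fits Section 9 read alone but not the Synopsis.

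**3. What a free choice would cost.** The plan has no power calculation to reproduce. The documents give N = 64 and 1:3 allocation in Stage 1, hence 16 v 48. The following are assumptions: 36 placebo non-responders in Stage 2 (18 v 18), equal correlation ρ between visits, equal variances, no missing data, two-sided 5%, and the same effect profile in both Stages.

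- Expected Z per SD of effect: Stage 1 √(16×48/64) = 3.464; Stage 2 √(18×18/36) = 3.000.
- Combined with equal weights: (3.464 + 3.000)/√2 = 4.571.
- Variance of the three-visit mean relative to one visit: (1 + 2ρ)/3. At ρ = 0.6 this is 0.733, square root 0.856, which is also the correlation between the two contrasts.
- Power = Φ(expected Z − 1.96); the other tail is negligible.

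At ρ = 0.6, day 7 Z = 4.571 × last effect, and average Z = 4.571 × mean effect / 0.856:

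| Effect at the three visits (SD) | Z, day 7 | Power | Z, average | Power |
|---|---|---|---|---|
| constant 0.6, 0.6, 0.6 | 2.74 | 78% | 3.20 | 89% |
| mild build-up 0.4, 0.5, 0.6 | 2.74 | 78% | 2.67 | 76% |
| build-up 0.2, 0.4, 0.6 | 2.74 | 78% | 2.13 | 57% |
| fading 0.6, 0.6, 0.3 | 1.37 | 28% | 2.67 | 76% |

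Under the null, the chance that at least one contrast is significant follows from the bivariate normal distribution with correlation √((1 + 2ρ)/3):

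| ρ | 0.4 | 0.6 | 0.8 |
|---|---|---|---|
| Correlation of contrasts | 0.775 | 0.856 | 0.931 |
| Type I error, better of the two | 8.0% | 7.4% | 6.7% |

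A separate calculation with SD 8 or 10 points, Stage 2 groups of 24 or 17, and ρ of 0.5 to 0.8 gave 6.7-7.7%. Both contrasts being significant in opposite directions had probability below 0.001% in every scenario, so disagreement means significant against not significant, never benefit against harm.

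**The case for a change.** The strongest reply is that Section 9 is the operative analysis text and names no contrast, that no passage states that day 7 is the 72-hour visit, and that naming an MMRM does not choose between a visit effect and an average. Some study team members know the assignments (Section 6.2), so prespecification carries weight, and one sentence would close the gap.

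The omission is real, and so is the possible difference in result: 28% against 76% power under the assumed fading profile is large. The claim that both contrasts comply with the whole plan does not stand, because the Synopsis sets a time point under the label of primary outcome. Nor does tying the secondary outcomes to 72 hours imply another time for the primary. That sentence says that the secondary outcomes will also be evaluated in the same analysis set, and the primary already has its time point in the Synopsis. Finally, the type I error figure describes an analyst who sees the results and then chooses, not one who follows the documents.

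**Conclusion.** The concern does not call for a change. The two descriptions are compatible, and an analyst who reads them together would test the MMRM treatment difference at the 72-hour visit after session 3 in each Stage. Writing that into Section 9 would record the choice without altering the analysis.

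Replacing day 7 by the visit average would be a trade-off and not a correction. With ρ = 0.6 and 36 Stage 2 non-responders, day 7 loses about 11 percentage points of power under a constant 0.6 SD effect (78% v 89%). It gains about 21 if the effect builds in thirds (78% v 57%) and loses about 48 if the effect halves by 72 hours (28% v 76%). The most that an undisciplined choice adds to type I error is about 2 to 3 percentage points for ρ between 0.4 and 0.8. The correlations, effect sizes, profiles and Stage 2 number are assumptions. They show that the contrasts can differ, not how often they would.

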4.2. Exclusion Criteria

- a) Schizophrenia
- b) Schizoaffective disorder
- c) Obsessive-compulsive disorder or panic disorder
- d) Active or recent substance abuse or dependence (in remission at least 1 year prior to the study; exception = nicotine use disorders)
- e) A diagnosis of personality disorder (confirmed by patient interview and medical chart review) that may interfere with the patient's ability to improve on nitrous oxide as determined by study investigator
- f) Acute medical illness that may pose subject at risk during nitrous oxide administration (neurological disorders or medical disorders including dementia, stroke, encephalopathy Parkinson's Disease, brain tumors, multiple sclerosis, seizure disorder, severe cardiac disease,

any disease known to affect drug metabolism and excretion, i.e. renal or liver disease) per P.I. discretion

- g) Active suicidal intention (inability to contract for safety)
- h) Active psychotic symptoms
- i) Patients with significant pulmonary disease and/or requiring supplemental oxygen
- j) Contraindication against the use of nitrous oxide: pneumothorax; bowel obstruction; middle ear occlusion; elevated intracranial pressure; chronic cobalamin and/or folate deficiency treated with folic acid or vitamin B₁₂; pregnant patients; breastfeeding women; previous administration of NMDA-receptor antagonists (e.g., ketamine); current electroconvulsive therapy treatment

5. Enrollment

[figure not shown]
Patients with a diagnosis of bipolar depression and history of resistance to treatment (as defined above) will be recruited. Patients will be screened, consented for participation and enrolled in the study by study team personnel. We aim to recruit a total of 64 patients with the diagnosis of treatment-resistant bipolar depression, defined as failure to respond to two or more adequate dose-duration trials of antidepressant medications by history and chart verification.

6. Methods

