6.1. Study Design (see summary figure below)

Prospective, randomized, placebo-controlled trial using the Sequential Parallel Comparison Design (SPCD) designed by PPD, a contract research organization. In the **first stage**, patients will be randomized (1:3 active [nitrous oxide] to placebo) to receive three 1-hour inhalation treatments every other day. Approximately 24-72 hours after the treatment session, patients will be assessed by the MADRS along with other scales as detailed below. Participants will also have follow-up visits/assessments performed approximately 1 and 2 weeks from the last inhalation session. The active treatment recipients from the **first stage** will receive a **second stage** of active treatment. All patients on placebo in the first stage (n \approx 48) will be re-randomized in the **second stage** (1:1 active to placebo) to three 1-hour treatments every other day, with the same follow-up visits/assessments as in Stage 1 (see study flow figure below). Throughout both stages group assignment will remain double-blinded to the participants and study raters conducting the assessments.

For ethical purposes, once the study blind has been broken those TRD subjects who were randomly assigned to receive successive placebo treatments will be offered an optional open label phase of active treatment (i.e., three 1-hour every other day inhalation treatments).

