6.2. Randomization

The group assignment will be randomly assigned (1:3 active treatment to placebo) for each participant in Stage 1 and 1:1 (active: placebo) in Stage 2 for those previously assigned to placebo. Participants randomly assigned to active treatment in Stage 1 will remain on active treatment in Stage 2. PPD, LLC will be aiding in the randomization of participants. Study raters will remain blinded along with the participants to group assignment until the end of Stage 2. The team responsible for the administration of the nitrous oxide treatment and other study team members not conducting ratings will know the group assignment and can provide this information to participants or other team members if needed (see below for more information in 6.3).

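### Does the missing definition of placebo non-response undermine the Stage 2 half of the primary test?

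*Combined protocol and SAP*

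**What the plan says.** Section 5 sets the size: "We aim to recruit a total of 64 patients". Section 6.2 allocates 1:3 active to placebo in Stage 1. For Stage 2, Section 6.1 re-randomises "All patients on placebo in the first stage", given as about 48. Section 6.2 has "1:1 (active: placebo) in Stage 2 for those previously assigned to placebo", and the Synopsis agrees: "participants assigned to placebo in Stage 1 will be randomized to three 1-hour treatments every other day". None of these three places mentions response or stratification by it.

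Section 9 describes the Stage 2 part of the full analysis set as follows: "In Stage 2, the placebo non-responders who were re-randomized and had at least one treatment dose", together with one efficacy assessment after baseline. The secondary outcomes use the same restriction ("placebo non-responders in Stage 2"). On the primary test, Section 9 states: "Stage-wise test statistics representing the active vs. placebo response will be combined with equal weights for each Stage".

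Three other statements bear on the gap. Section 7.2 names the MADRS as the primary outcome and has blinded raters score patients about 30 minutes before treatment and again afterwards. Section 7.1 confines the efficacy analysis to the two 24-hour measures and the one 72-hour measure, and treats weeks 1 and 2 as preliminary information on durability. The Synopsis requires a baseline assessment before each treatment series.

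**The concern.** Two things look wrong. First, the randomised Stage 2 group (all placebo patients) is not the analysed group (non-responders only), which suggests that the protection of randomisation has been lost. Second, non-response has no stated scale, threshold, reference baseline or visit. Two statisticians could build different Stage 2 sets from the same data, and with equal stage weights that set drives half of the primary statistic. If the rule were settled once outcomes were known, the type I error would not be controlled. The size of the set, and so the power, would also be uncertain, and Section 9 offers no power calculation that would fix an expected number.

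**Working it through.** **The plan's own figure.** 64 × 3/4 = 48 placebo patients in Stage 1, which matches the stated number. Re-randomised 1:1, this gives 24 per arm.

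**Is the mismatch a defect?** Section 9 speaks of non-responders *among* those re-randomised, so its set is a subset of the group in Sections 6.1 and 6.2. The passages agree. Membership depends only on Stage 1 scores, or at the latest on the rating before the first Stage 2 inhalation. Stage 2 treatment cannot influence it, and the arms remain randomly allocated within the subset. Re-randomising everyone and analysing the non-responders is a legitimate form of this design.

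**Is the information available?** Yes. The MADRS is rated about 72 hours after the third Stage 1 session and again before Stage 2 treatment. Only the classification rule is unwritten.

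**Type I error.** The documents give no MADRS mean or SD, so these inputs are assumptions: baseline 30 (SD 5), change SD 8, mean placebo change −4 or −8, correlation 0.7 between the 72-hour score and the Stage 2 baseline. With no treatment effect, 16 v 48 in Stage 1 and 24 v 24 in Stage 2, the statistic is Z = (Z1 + Z2)/√2, tested two-sided at 5%. Six rules were tried: improvement below 50% or below 25% at 72 hours, the same two at the Stage 2 baseline, Stage 2 baseline MADRS above 20, and all patients.

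| How the rule is chosen | Two-sided type I error |
|---|---|
| Any one rule, fixed | 4.5% to 5.2% |
| Better of the two 72-hour cut-offs, picked on results | about 7% |
| Best of all six, picked on results | about 9% to 11% |

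**Size of the set and detectable effect.** Let r be the placebo response rate. The analysed number is n = 48 × (1 − r). With s1 = √(1/16 + 1/48) = 0.289 and s2 = √(4/n), the effect detectable with 80% power (two-sided 5%, both assumed) is 2.802 / [(1/s1 + 1/s2)/√2].

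| r | n | Detectable effect (SD) | Combined power at an assumed 0.5 SD |
|---|---|---|---|
| 0% | 48 | 0.57 | 69% |
| 5% | 45.6 | 0.58 | 68% |
| 25% | 36 | 0.61 | 63% |
| 50% | 24 | 0.67 | 55% |

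Only the 5% rate stands in the documents (1 of 20 after placebo in the unipolar pilot, Preliminary Data). The other rates are assumed.

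**Would stratifying Stage 2 by response help?** Without it, the split of n non-responders between two arms of 24 is hypergeometric. The expected value of 1/nA + 1/nB is then compared with 4/n, its value under an even split. For n = 46 these are 0.0870 and 4/46 = 0.0870, a difference of 0.1%. For n = 24 they are 0.1705 and 4/24 = 0.1667, a difference of 2.3%. With n = 36, the arms differ by four or more patients about 32% of the time, but a 20:16 split gives 1/20 + 1/16 = 0.1125 against 4/36 = 0.1111, a variance only 1.3% higher.

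**The case for a change.** The strongest case for a change is that the primary analysis set cannot be built from the text alone, and that writing the rule down would cost almost nothing. Blinding does not fully close the gap either, because Section 6.2 lets team members who do not rate patients know the assignment. Even if the option of analysing everyone is struck out, since Section 9 excludes it, picking the best of the remaining five rules still gave an error of about 9% to 10% in simulation. The cut-off also decides which patients the Stage 2 effect describes. A 25% rule at 72 hours could leave as few as about 23 of 48, whereas a 50% rule leaves roughly 37 to 44.

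It stands that the definition is missing from the visible text. The study flow figure is not reproduced here and might hold a criterion, but nothing in the text says so.

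The rest carries less weight. The inflated error rates presuppose that someone tries several rules and keeps the favourable one; they do not describe the planned test. Several of the six rules also sit badly with the plan. One contradicts Section 9 outright. Section 7.1 favours the 72-hour visit over later ones, although it does not address classification explicitly. The MADRS at the end-of-stage visit is the obvious basis, which leaves only the cut-off to settle, and every cut-off gives a valid test.

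**Conclusion.** No change follows. Analysing a subset of the re-randomised patients is sound because membership is settled before Stage 2 treatment. The undefined term is a real omission, but one that an analyst fills in the ordinary way: one MADRS rule at the end of Stage 1, chosen without reference to Stage 2 results. Done like that, the test holds its level, at 4.5% to 5.2% under the assumed MADRS distribution. The choice of rule affects power and the population described, not validity. At the only placebo response rate in the documents the detectable effect moves from 0.57 to 0.58 SD, and it reaches 0.67 SD only if half of the placebo patients respond.

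The possible additions bring little. Stratifying the second randomisation would remove about 0.1% to 2.3% of the Stage 2 variance for 46 down to 24 analysed patients, and validity does not need it. A sensitivity analysis of all re-randomised placebo patients would leave the primary result as it is. The conclusion assumes that the rule is not selected on outcomes. If it were, the error would be about 7% for a choice between the two 72-hour cut-offs and about 9% to 11% for a free choice among all six rules.

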7.2. Assessment of Treatment Efficacy

The effects of the treatment will be assessed using standard scales used for mood assessments in psychiatry, psychosis, and disassociation:

- a) the MADRS (**Primary Outcome**) to assess change in depression;
- b) the Hamilton Depression Rating Scale-17 item (Ham-D17), secondary measure of depression;
- c) Young Mania Rating Scale (YMRS) to assess emergence of mania/hypomania (patients with YMRS scores > 12 will be removed from the trial and recommended for follow-up treatment per Psychiatry P.I., i.e., nitrous oxide treatments discontinued);
- d) the Profile of Mood States, 2nd edition (POMS 2) to assess for rapid/instantaneous changes in mood/affect;
- e) the Quick Inventory of Depressive Symptomatology- Self Report (QIDS –SR) patient-rated depression measure;
- f) Clinician Administered Dissociative States Scale (CADSS) for emergence of disassociation;
- g) the Brief Psychiatric Rating Scale (BPRS) to assess psychotic or hallucinogenic behavior; and
- h) Scale for Suicidal Ideation (SSI) to assesses for emergence of suicidal thinking.

Patients will be assessed approximately 30 minutes before treatment, and approximately 1 hour and 24-72 hours after treatment by one of the expert psychiatry study team members who will be blinded to the study group assignment.

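### Section 9 gives the primary MMRM no baseline MADRS term; adding each Stage's own baseline is a cheap precision improvement of modest, uncertain size

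*Combined protocol and SAP*

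**What the plan says.** Section 9 (Data Analysis) defines the primary outcome: it "is the change from baseline in MADRS scores during the first study week in each Stage of the SPCD study". It then gives the model: "A mixed model for repeated measurements (MMRM) with an unstructured variance-covariance matrix will be used for the primary efficacy analysis". The next sentence turns to missing data. Between them, no treatment, visit, interaction or baseline term is listed. The Stages are then joined: "Stage-wise test statistics representing the active vs. placebo response will be combined with equal weights for each Stage".

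The Statistical Methodology row of the Synopsis names only a repeated-measures mixed model. Section 6.2 gives allocation ratios ("The group assignment will be randomly assigned (1:3 active treatment to placebo) for each participant in Stage 1", then 1:1 in Stage 2) and no stratification by severity. Baseline severity therefore enters the plan only by subtraction.

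On sample size, Section 6.1 re-randomizes about 48 Stage 1 placebo patients, but Section 9 narrows the Stage 2 analysis set: "In Stage 2, the placebo non-responders who were re-randomized and had at least one treatment dose" and one post-baseline assessment contribute. No response threshold or expected number of non-responders is given.

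**The concern.** A change-score model without baseline fixes the slope of follow-up on baseline at 1. If the true slope is lower, as regression to the mean usually makes it, the unadjusted treatment contrast carries baseline noise that a covariate would remove. With 16 active patients in Stage 1 and at most 24 per arm in Stage 2, avoidable noise matters more than it would in a large trial. Because no terms are listed, the choice between an adjusted and an unadjusted model also stays open until results can be seen. What is at stake is precision and pre-specification, not bias.

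**Working it through.** **Inputs from the documents.** N = 64. Allocation 1:3 gives 64 × 1/4 = 16 active and 64 × 3/4 = 48 placebo, which reproduces the figure of about 48 in Section 6.1. Stage 2 at 1:1 gives at most 24 vs 24.

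**Assumptions, because the documents give no SD or correlation.** r = baseline/follow-up correlation, 0.3 to 0.6. k = baseline SD / follow-up SD, taken as 0.6, 0.8 or 1. Entry at MADRS >20 (Section 4.1) restricts the baseline range and makes a low k plausible in Stage 1. Stage 2 has 48, 36 or 24 patients (0%, 25% or 50% placebo response). Two figures in Section 2 serve as anchors: 5% placebo response in the pilot gives 48 × 0.95 ≈ 46, and 25% response to an adjunctive antidepressant gives 48 × 0.75 = 36.

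**Formula.** With complete data and a baseline-by-visit term, the unstructured MMRM contrast at a visit equals the one-visit regression. With equal slopes and variances in both arms:

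adjusted variance / unadjusted variance = (1 − r²) / (1 + k² − 2kr) × [1 + 1/(n − 4)]

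The bracket is the average finite-sample cost of estimating one slope. The true slope is r/k. When it equals 1, the first factor is 1 and only the cost remains.

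**Average cost when baseline adds nothing.** n = 64: 1/60 = 1.7%. n = 48: 1/44 = 2.3%. n = 36: 1/32 = 3.1%. n = 24: 1/20 = 5.0%. Simulation (40,000 runs per design) gave 1.7%, 2.2%, 3.1% and 4.8%.

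**Stage 1 variance ratio (n = 64).** Example, k = 0.8 and r = 0.3: 0.91/1.16 = 0.784, times 1.0167 = 0.798.

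| k | r = 0.3 | r = 0.4 | r = 0.5 | r = 0.6 |
|---|---|---|---|---|
| 0.6 | 0.925 | 0.970 | 1.003 | 1.017 |
| 0.8 | 0.798 | 0.854 | 0.908 | 0.957 |
| 1 | 0.661 | 0.712 | 0.762 | 0.813 |

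In Stage 1 the unadjusted model is as good or slightly better only for r of about 0.49 to 0.69 at k = 0.6, or 0.71 to 0.86 at k = 0.8.

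**Equal-weight combined Z.** If the effect and SDs are equal in both Stages, expected Z is proportional to 1/SE₁ + 1/SE₂. Since 1/16 + 1/48 = 1/24 + 1/24 = 1/12, the two Stages count equally at 24 vs 24. Example, k = 0.8 and r = 0.3: 1/√0.798 = 1.119 and 1/√0.802 = 1.117, mean 1.118, so +11.8%. Change from adding baseline, for r = 0.6 to r = 0.3:

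| Stage 2 | k = 0.6 | k = 0.8 | k = 1 |
|---|---|---|---|
| 24 vs 24 | −1.0% to +3.8% | +2.1% to +11.8% | +10.7% to +22.8% |
| 18 vs 18 | −1.1% to +3.6% | +1.9% to +11.6% | +10.5% to +22.6% |
| 12 vs 12 | −1.5% to +3.3% | +1.6% to +11.2% | +10.1% to +22.2% |

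With k = 0.6 in Stage 1 and 0.8 in Stage 2, the range at 24 vs 24 is +0.5% to +7.7%.

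**Unequal slopes in Stage 1.** Simulation at 16 vs 48 (60,000 runs; assumed residual SD 8, baseline SD 5 to 8) gave these adjusted/unadjusted variance ratios:
- active slope 1.0, placebo 0.5: about 1.035 to 1.065
- active slope 1.2, placebo 0.6: about 1.05 to 1.10
- active slope 0.5, placebo 1.0: about 0.95 to 0.99
- both slopes 1: about 1.017

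A common-slope model weights its slope toward the larger placebo arm, so the sign depends on which arm is steeper.

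**The case against.** The strongest objection is that the benefit rests on inputs the plan does not give. The one clue, entry at MADRS >20, points to a narrow baseline; at k = 0.6 in both Stages the change in Z is close to nil. The non-responder restriction may also narrow the Stage 2 baseline. The Abstract calls the trial a pilot, and an unadjusted estimate is unbiased. All of this stands, and it limits the claim to a modest, uncertain gain. It does not remove the case for settling the terms in advance.

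Three stronger readings are tempting, and none is supported.

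- *The cost of adjusting is at most 2% to 5%.* Those figures are averages over allocations. With an uninformative baseline, the realised cost exceeds 5% in about 8% of allocations at n = 64 and 31% at n = 24 (95th percentiles 6.4% and 19.5%). The 5% end needs at least 24 Stage 2 patients; at 20 the average is 6.3% and at 16 it is 8.3%. Unequal slopes can add to this.
- *The baseline is undefined, because assessments precede every treatment.* Section 7.1 has "Assessments will be performed before and after (approximately 1 and 24 hours) each treatment" and Section 7.2 has "Patients will be assessed approximately 30 minutes before treatment", but neither calls these baselines. The Study Design row of the Synopsis attaches the label to the start of each series ("Assessments will be performed prior to each treatment series (baseline"), and Section 9 applies change from baseline within each Stage. Restating this in Section 9 is tidying.
- *A gain of 10% to 23% is to be expected.* That needs a baseline SD equal to the follow-up SD in both Stages, which nothing in the documents supports.

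**Conclusion.** The omission is real: Section 9 includes no baseline MADRS term, and no other section supplies one. A literal run is an unadjusted change-score MMRM, valid but usually less precise than the adjusted model. A reader might infer that the plan deliberately chose an unadjusted analysis, or that its estimate would be biased. The text is silent on the first, and randomization rules out the second.

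Over the assumed ranges the expected combined Z moves between a loss of about 1.5% and a gain of about 23%, with the upper part least supported. These figures assume complete data, equal slopes and variances in both arms, the same treatment effect in both Stages, and 24 to 48 Stage 2 patients. If the active-arm slope is steeper, Stage 1 could instead lose about 4% to 10% in variance. The change is worth making because it is nearly free and settles the model in advance, not because the present plan is invalid.

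**What to change.** Before unblinding, state in Section 9 that each Stage's MMRM for change in MADRS contains treatment, visit, treatment-by-visit, own-Stage baseline MADRS and baseline-by-visit, with the unstructured covariance already chosen. Add a clause that own-Stage baseline is the assessment before that Stage's treatment series, consistent with the Synopsis.

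This takes about two sentences. It uses data already collected and changes no visit, sample size or procedure. The statistical price is a few degrees of freedom and, if baseline proves uninformative, the variance cost set out above.
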